#### 4.3 Subject Recruitment and Screening

Subjects are recruited by qualified and trained site personnel when they are identified as experiencing either a) at least two recurrences of CDI after a primary episode (i.e., at least three episodes) and have completed at least two rounds of standard-of-care oral antibiotic therapy or b) had at least two episodes of severe CDI resulting in hospitalization. Potential subjects are to be fully informed as to this study's purpose, requirements, anticipated risks, etc., and are to be given the chance to review the informed consent form and receive satisfactory answers to all questions. Subjects must then sign the study-specific, IRB/REB-approved Informed Consent Form and HIPAA Form (if applicable), which is the point of study enrollment.

Subjects are eligible to receive study treatment upon confirmation that they have met all inclusion/exclusion criteria listed in Sections 4.1 and 4.2. Subjects must discontinue their antibiotics for 24-48 hours prior to receiving the first study enema.

#### 4.4 Subject Withdrawal or Termination

A subject's study participation is considered complete after the final telephone call is conducted 24 months after completion of study treatment with RBX2660.

A subject may withdraw or be withdrawn from the study prematurely for the following reasons:

- Withdrawal of consent by subject
- Lost to follow-up
- Failure to comply with study requirements
- Termination of study by the sponsor
- Death
- Other (to be specified).

The reason for termination is recorded on the Study Exit eCRF. In the event that a subject withdraws from the study, every attempt should be made to have the subject return for an early withdrawal visit and to complete the 3-, 6-, 12-, and 24-month telephone calls. [REDACTED]

[REDACTED]

## 5.0 RBX2660

### 5.1 RBX2660 Description

RBX2660 microbiota suspension 50 g/150 mL in an enema bag. Each bag of RBX2660 provides one enema (one dose). [REDACTED]

[REDACTED] One study treatment consists of two doses of RBX2660 administered  $7 \pm 2$  days apart.

### 5.3 Rebiotix Kit Description

[REDACTED]

- [REDACTED]
- [REDACTED]
- [REDACTED]
- [REDACTED]

### 5.4 Treatment Regimen

See Section 6.0 for the Schedule of Study Procedures and a full description of them.

**5.5 Subject Compliance Monitoring**

Subjects are assessed at an in-office visit at 8 weeks and via telephone calls from the study coordinator at 1, 2, 3, and 4 weeks and 3, 6, 12, and 24 months after completion of study treatment with RBX2660. See Section 6.0 for follow-up assessments and phone calls, and Section 4.4 for subject withdrawal/termination.

█ [REDACTED]

**5.7 Preparation of RBX2660**

Instructions for Use with detailed directions for RBX2660 preparation and administration are in each Rebiotix Kit.

**5.8 Packaging**

[REDACTED]

█ [REDACTED]

[REDACTED]

[REDACTED]

[REDACTED]

[figure not shown]

## 6.0 Study Procedures

### 6.1 General Information

Study information is collected on study-specific electronic case report forms (eCRFs) by the site. Study monitoring occurs at regular intervals to ensure the protection of subject rights and safety, data integrity and accuracy, and proper study conduct in compliance with the protocol and applicable regulations including 21 CFR 50 and 312 and ICH E6 GCPs. The study-required procedures for treatment subjects are to be conducted as shown in Table 6-1 and illustrated in Figures 2 and 3.

CONFIDENTIAL

[figure not shown]

**Figure 2: Study Design**

Rebiotix Inc

██████████  
RBX2660 (microbiota suspension)  
Protocol 2015-01  
v5 20 Jan 16

**Figure 3: Study Procedures and Timeline**

**6.2 Informed Consent**

All subjects must sign the study-specific IRB/REB-approved Informed Consent Form and HIPAA Form (if applicable); see Section 4.3. The original is to be stored in the subject's medical record unless otherwise indicated by site procedures and a copy of the signed Form is to be placed in the subject's study file. A copy of the Form is to be given to the subject for his/her records.

**6.3 Subject Diary**

Subjects are to complete the Subject Diary from the time of enrollment until seven days after the last study treatment enema (second dose). The Diary serves as a tool for the subject to record pre- and post-treatment health and information that may indicate the reoccurrence of CDI and adverse events. The pre-treatment Diary information is recorded by the subject from the day of enrollment to the day before the first study treatment and is reviewed and collected at the baseline visit. The post-treatment Diary pages are given to the subject on the day of the first study treatment and are to be collected at the second enema visit (Visit 3) and at the 8-week office visit (Visit 4). The study coordinator reviews the contents of the Diary and records the relevant information in the study database. All pages of the Diary are required to be collected, reviewed and entered into the study database.

**6.4 Visit 1: Screening Visit**

At the screening visit, subjects are told about the study and informed consent (and HIPAA Form, if applicable) is (are) obtained. Standard demographics (gender, ethnicity, date of birth, etc.) and a detailed medical history are collected. Blood for the absolute neutrophil count is obtained. If applicable, a urine-dipstick pregnancy test is taken. Vital signs are assessed, concomitant medications are recorded, and AEs/SAEs are assessed. Completion of the Subject Diary is explained and how to complete it is demonstrated; see Section 6.3. Remind subjects to bring completed Diary pages with them at Visits 2, 3, and 4. Inclusion/exclusion criteria are assessed. A baseline Form SF-36 is administered.

[REDACTED]  
[REDACTED] Antibiotics for the control of CDI  
symptoms are prescribed or continued [REDACTED]  
[REDACTED]  
[REDACTED]  
[REDACTED]

**6.4.1 Stool Samples [REDACTED]**

Subjects are requested to provide stool samples to Rebiotix at screening; in between Visits 2 and 3; at 1, 4, and 8 weeks after Visit 3; around the time of the 6-, 12-, and 24-month phone calls; if CDI reoccurs prior to 56 days after completing study treatment and if CDI occurs any time during the study participation. [REDACTED]

[figure not shown]
[REDACTED]

**6.5 Visit 2: Baseline Visit and First Enema**

The baseline visit is performed on the day of the first enema administration. A modified physical exam (no genitourinary exam unless medically indicated) is performed to establish baseline health status, vital signs, and document pre-existing medical conditions. Blood and stool samples are collected per Table 6-2 and are tested at the site's CLIA-approved lab to establish baseline health should an adverse event occur in the future. [REDACTED]

[REDACTED]

**Table 6-2:**

The pre-treatment Subject Diary is reviewed and collected and a post-treatment Subject Diary is given to the subject; completion instructions are to be reviewed with the subject. Inclusion/exclusion criteria and completion of the washout period are confirmed. Recurrence of CDI symptoms is assessed, concomitant medications are recorded and AEs/SAEs are assessed. Prior to administration of each dose of RBX2660, a female subject of childbearing potential is required to undergo a urine-dipstick pregnancy test to confirm that she is not pregnant. RBX2660 is administered via enema per the Instructions for Use and standard site procedure by the authorized RBX2660 Administrator; see section 5.9.3.

[REDACTED]  
[REDACTED]  
[REDACTED] The subject is sent home after a review of the Subject Diary instructions, instructions to call the study coordinator if CDI symptoms reoccur, and an appointment for the next enema of RBX2660.

**6.6 Visit 3: Second Enema**

The subject returns to the site for the second enema of RBX2660  $7 \pm 2$  days after the first enema [REDACTED]

[REDACTED] Recurrence of CDI symptoms is assessed, concomitant medications are recorded and AEs/SAEs are assessed. Prior to administration of RBX2660, a female subject of childbearing potential is required to undergo another urine-dipstick pregnancy test to confirm that she is not pregnant. The Subject Diary is reviewed to ensure it is being completed properly and the first page of the post-treatment Diary should be collected if available. RBX2660 is administered via enema per the Instructions for Use and standard site procedure by the authorized RBX2660 Administrator. [REDACTED]

[REDACTED]  
[REDACTED]  
[REDACTED]  
[REDACTED] The subject is sent home after a review of the Subject Diary instructions, instructions to call the study coordinator if CDI symptoms reoccur, and an appointment for the 8-week follow-up visit.

**6.7 Weekly Telephone Assessments**

Study coordinators will make weekly phone calls during weeks 1-4 after completing study treatment with RBX2660. The purpose of the calls is to assess for AEs including SAEs and the onset of new chronic diseases, recurrence of CDI and an update of concomitant medications. [REDACTED]

[REDACTED]  
[REDACTED]  
[REDACTED]  
[REDACTED]

**6.8 8-Week Office Visit (Visit 4)**

Subjects return to the study site for the 8-week follow-up visit after completing study treatment with RBX2660. [REDACTED]

[REDACTED] At this visit, reoccurrence of CDI and adverse event information is assessed, a review of medication changes and pre-existing conditions is conducted, and the SF-36 Form is administered. The assessment of pre-existing conditions includes discussion with the subject to determine if the condition is improved, unchanged, worsened or resolved since completion of study treatment. The Subject Diary is collected and reviewed with the subject. [REDACTED] If CDI reoccurrence is suspected < 56 days after completing study treatment, the investigator assesses for recurrence using the four criteria in Section 3.6. The need for retreatment for *C. difficile* infection in the absence of a positive stool test for *C. difficile* will be made by the study investigator so that the appropriate treatment of the subject can be quickly administered in the case of failure to avoid serious adverse events, including hospitalization or death. If the subject does not have reoccurrence of CDI before 56 days after completing study treatment, s/he is considered a treatment success (see Section 3.5). [REDACTED]

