### 2.4 Secondary Endpoints

1. The frequencies and severity grades of solicited AEs from the first day of assigned study treatment through seven days following the last enema of assigned study treatment will be collected.
2. Adverse events, including serious adverse events and the onset of new chronic diseases, will be collected at in-office visits at 1, 4 and 8 weeks and at 3-, 6-, and 12-month calls; they will be categorized by frequency, severity, seriousness, and causality.
3. Serious adverse events and new onset of chronic diseases will be collected at a telephone call at 24 months and will be categorized by frequency, severity, seriousness, and causality.
4. Frequencies of major complications of CDI including death, septic shock, toxic megacolon, colonic perforation, emergency colectomy, or ICU admission will be collected through the 24-month telephone assessment.
5. The effect of RBX2660 on pre-existing conditions other than recurrent CDI will be assessed by comparing the change in the condition throughout the course of the study.
6. SF-36 scores recorded at the Week 8 visit will be compared to scores recorded at the screening visit.
7. Efficacy of *C. difficile* anti-infection therapies administered to confirmed treatment failures will be compared to each other for the rates of success at resolving CDI diarrhea for at least 56 days after completion of the anti-infection therapy.

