#### 3.2 Study Design

This is a prospective, multicenter, open-label study assessing RBX2660 as an adjunct to antibiotics for the treatment of recurrent CDI. Up to approximately 150 subjects will be enrolled in this study. Efficacy of RBX2660, measured by the recurrence-free rate of CDI diarrhea without the need for retreatment with *C. difficile* anti-infective therapy or fecal transplant through 56 days after completion of study treatment with RBX2660, will be evaluated by comparing the recurrence-free rate observed in the study population to the recurrence-free rate identified from antibiotic-treated historical controls. Subjects who meet all inclusion and exclusion criteria, including having a positive *C. difficile* test within 60 days prior to enrollment and experiencing either a) at least two recurrences after a primary episode and have completed at least two rounds of standard-of-care oral antibiotic therapy or b) have had at least two episodes of severe CDI resulting in hospitalization prior to enrollment, will receive treatment with RBX2660. One study treatment consists of two RBX2660 enemas administered  $7 \pm 2$  days apart (no antibiotics between doses); the second enema may be administered sooner if CDI diarrhea reoccurs in less than 7 days. Subjects will already be taking or will start a course of antibiotics to control recurrent CDI diarrhea at the time of enrollment, [REDACTED]

[REDACTED] An in-office follow-up visit will occur at 8 weeks after completing study treatment for the assessment of AEs, efficacy, collection of the Subject Diary, and blood tests. Telephone assessments for adverse events including SAEs and the new onset of chronic diseases and CDI symptoms will occur at weeks 1, 2, 3, and 4 and at 3, 6, and 12 months after completing study treatment. Assessment of serious adverse events and the new onset of chronic diseases will occur via phone call at 24 months after completing study treatment. Subjects will

keep a detailed Subject Diary to allow for assessment of solicited adverse events (see Section 7.1.3) from the date of enrollment to 1 week after completing study treatment. Treatment failures (as determined by the site investigator at the time of CDI recurrence) are eligible to receive another therapy deemed most appropriate by their study investigator; see “Management of Treatment Failures,” below.

[REDACTED]

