**6.9 3-, 6-, 12-, and 24-Month Telephone Assessments**

Subjects receive a telephone assessment for adverse events, including serious adverse events and the new onset of chronic diseases at 3, 6, and 12 months; and an assessment of pre-existing conditions, serious adverse events and the new onset of chronic diseases at 24 months after completion of study treatment with RBX2660. These phone calls must occur within the window specified in Table 6-1; calls [REDACTED]

The assessment of pre-existing conditions includes discussion with the subject to determine if the condition improved, unchanged, worsened or resolved since completion of study treatment. Information on concomitant medications is updated as needed. [REDACTED]

[REDACTED] Adverse events and the new onset of chronic diseases are to be recorded and reported as required in Section 7.0 [REDACTED]

[REDACTED] The last phone call occurs at 24 months after completion of study treatment with RBX2660. [REDACTED]

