### 7.1.4 Preexisting Condition

A preexisting condition, including abnormal physical exam findings, is one that is present at the start of the study and is to be recorded at the time of the screening or baseline visits. A preexisting condition is to be recorded as an adverse event if the frequency, intensity or the character of the condition worsens during study participation. They are also to be assessed at the 3-, 6-, 12-, and 24-month telephone assessments; See Section 6.9.

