## 7.2 Assessment of Efficacy

The primary efficacy parameter is treatment success, defined as the absence of CDI diarrhea without the need for retreatment with *C. difficile* anti-infective

therapy or FT through 56 days after the completion of study treatment (Visit 3). Some subjects may continue to have short bouts of diarrhea before the 56-day time point, but most if not all will be resolved within 30 days after receiving RBX2660. The efficacy assessment will occur at the 8-week office visit.

[REDACTED]  
[REDACTED]  
[REDACTED]

[REDACTED] See Sections 6.10 and 8.0 of this protocol and the separate Statistical Analysis Plan for additional details on the efficacy assessment.

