4.7 Treatment Arms

The open-label study consists of a single prospective treatment arm and historical control group, as described below.

- One treatment with RBX2660: one treatment consists of two enemas of RBX2660 administered 7 ± 2 days apart (the second enema may be administered sooner if CDI diarrhea reoccurs in less than 7 days). [REDACTED]
- Historical control group chosen from a retrospective chart review.

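### Change in pre-existing conditions is rated from the second enema, so a change completed between the two enemas is recorded as unchanged

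*Protocol*

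**What the plan says.** Under endpoint 5 (Protocol 2.4, repeated in Protocol 8.2.2 and SAP 3.4), the effect of RBX2660 on conditions other than recurrent CDI "will be assessed by comparing the change in the condition throughout the course of the study". No reference visit is named.

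The starting status is a pre-treatment one. Protocol 7.1.4 defines the term: it "is one that is present at the start of the study and is to be recorded at the time of the screening or baseline visits". Protocol 6.5 adds that the physical examination at the baseline visit documents these conditions.

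The follow-up question uses a different reference. At Visit 4 staff are to "determine if the condition is improved, unchanged, worsened or resolved since completion of study treatment" (Protocol 6.8). For the calls they are to "determine if the condition improved, unchanged, worsened or resolved since completion of study treatment" (Protocol 6.9), and SAP 6.4.3.3 repeats this.

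Protocol 7.2 identifies the reference point when it describes the efficacy period as running through "56 days after the completion of study treatment (Visit 3"; Visit 3 is the second enema. As to its distance from the first dose, SAP 4.7 states that "one treatment consists of two enemas of RBX2660 administered 7 ± 2 days apart", and Protocol 3.2 adds that "the second enema may be administered sooner if CDI diarrhea reoccurs in less than 7 days".

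**The concern.** The subject has already been exposed to RBX2660 at the reference point. If a joint condition, say, eases on day 3 after the first enema and stays better, the literal answer at 8 weeks is that it has not changed since treatment was completed. The same answer is due at every later call that asks. Objective 2 asks about exactly this kind of change, and the form would not show it.

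The status at Visit 3 is also not visibly recorded. The schedule in SAP 6.1 marks the review of pre-existing conditions only at Visit 4 and at the 3- to 24-month calls, and the visible text of Protocol 6.6 lists no such review at Visit 3. The subject must compare with a remembered state, up to two years later, although a written pre-treatment record exists.

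The other measures in the study do not start this late. SF-36 change is taken from screening (Protocol 2.4, SAP 8.7.2), and adverse events are treatment-emergent from the initial treatment date (SAP 6.4.2.4).

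**Working it through.** The documents give no sample size, rate or test for endpoint 5, so there is no stated figure to reproduce. The check has three parts.

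**1. Which changes the question misses.** The table compares the literal answer at Visit 4 under each reference, for a status that then holds unless stated.

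| Course of the condition | From Visit 3 (as written) | From screening/baseline |
|---|---|---|
| Improves or resolves between enemas | unchanged | improved or resolved |
| Improves between enemas, improves further afterwards | improved | improved |
| Improves only after Visit 3 | improved | improved |
| Improves between enemas, back to its starting level afterwards | worsened | unchanged |
| Worsens between enemas | unchanged (but an AE) | worsened |
| Worsens between enemas, back to its starting level afterwards | improved | unchanged |

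The answers differ only where a change is completed, or is later reversed, relative to the gap between the enemas. Worsening in the gap has a second route. Protocol 7.1.4 and SAP 6.4.2 make it an AE, Protocol 5.4's referenced procedures and Protocol 7.1.5 collect AEs from consent, and AEs are assessed at Visit 3 itself (Protocol 6.6). Improvement and resolution have no such route, so the loss falls mainly on them and will usually understate benefit. The last row is an exception.

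**2. How long the interval is.** Inputs: a gap g of 7 ± 2 days, so 5 to 9 (SAP 4.7), or shorter if the second enema is brought forward (Protocol 3.2); Visit 4 at 56 ± 7 days after Visit 3 (SAP 6.1); calls at 3, 6, 12 and 24 months after Visit 3. A month is taken as 30.44 days, which is an assumption.

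Share of the time since the first dose that lies before the reference point = g / (g + follow-up).

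| Assessment | g = 7 | Range |
|---|---|---|
| 8 weeks | 7/(7+56) = 11.1% | 5/(5+63) = 7.4% to 9/(9+49) = 15.5% |
| 3 months | 7/(7+91.3) = 7.1% | 5.2% to 9.0% |
| 6 months | 7/(7+182.6) = 3.7% | 2.7% to 4.7% |
| 12 months | 7/(7+365.3) = 1.9% | 1.4% to 2.4% |
| 24 months | 7/(7+730.5) = 0.95% | 0.7% to 1.2% |

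The 8-week range uses the visit window as well as the gap; the call ranges use gaps of 5 and 9 days at the nominal date. With a screening/baseline reference, no post-dose time precedes the reference.

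These are shares of time. The share falls with follow-up, but a change completed in the gap is missed at every assessment. If p is the true proportion of conditions that change and e the share of those changes completed in the gap and maintained, the question shows p × (1 − e). The fraction lost is simply e, and the documents say nothing about e.

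**3. Subjects with one enema.** The Safety Population needs only some RBX2660 treatment, and SAP 6.3 foresees subjects who did not complete two enemas. For them the reference could mean the only enema received or a point never reached. Under the first reading, a summary would mix subjects rated from the first enema with subjects rated from the second.

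**The case against.** The strongest case on the other side is that this is a small wording matter.

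- **The interval is short, and most change falls outside it.** This stands. A reader might infer that endpoint 5 cannot measure what it claims, or that every effect of the first enema is missed. Neither follows. A first-dose effect that appears or continues after Visit 3 is still rated, and so is any effect of the second dose.
- **Harm is covered.** This largely stands. Worsening between the enemas goes into the AE data. It does not help improvement or resolution.
- **Protocol 7.1.4 is not contradicted.** This stands. An AE records worsening at any time, while the four-category question records status against a reference point. The two tables can differ for one subject even with a pre-dose reference, for example when a condition worsens and then recovers.
- **The analysis may deal with it.** The SAP text after 8.6.2.2 is redacted, as are parts of Protocol 6.8 and 6.9, and the eCRF is not among the documents. The assessment is also described as including a discussion, so it may cover more than this question. It therefore cannot be said that no analysis could compensate. But the visible question yields a category tied to a date, and that category cannot be re-dated afterwards.
- **Little depends on it.** This stands. It is one of seven secondary endpoints in an open-label, single-arm study, with no visible test or decision rule attached.

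**Conclusion.** The point holds in a limited form. The stated reference is the second enema, it is the same in Protocol 6.8, Protocol 6.9 and SAP 6.4.3.3, and it does not match an endpoint that covers the whole study. It places some subjects in the wrong category: improvement or resolution completed in the 5 to 9 days between the enemas is rated as unchanged.

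The loss is partial and falls mainly on benefit. Its size in effect terms is unknown. A reader might assume that 20% of conditions change and that 25% to 50% of those changes are complete before Visit 3, so that 15% or 10% would show and a quarter to a half of the effect would be lost. That result only restates the assumed 25% to 50%, for which the documents offer no support. What they do support is the share of time: about 11% at 8 weeks, falling to about 1% at 24 months.

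The conclusion rests on reading completion of study treatment as Visit 3, as Protocol 7.2 does, and on the question being asked as written. The correction is worth making because it costs almost nothing and lets the endpoint answer its own question.

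How often the question is asked is a separate inconsistency. Protocol 6.9 names the assessment of pre-existing conditions only for the 24-month call, while Protocol 7.1.4, SAP 6.1 and SAP 6.4.3.3 place it at 3, 6, 12 and 24 months.

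**What to change.** - In Protocol 6.8 and 6.9, SAP 6.4.3.3 and any matching eCRF prompt, replace the reference to completion of treatment with: *compared with the status recorded at screening/baseline, before the first enema*. This also gives subjects with one enema a defined reference.
- Name the same reference in endpoint 5 (Protocol 2.4 and 8.2.2, SAP 3.4).
- Flag answers already collected against Visit 3 and do not merge them silently with later ones.
- Reconcile Protocol 6.9 with Protocol 7.1.4 and SAP 6.1 and 6.4.3.3 on which calls include the assessment.

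The cost is an amendment to the wording and to any eCRF prompt. The re-anchoring needs no extra visit, question or test and does not touch treatment.

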
Study Dosing
	
A study treatment consists of two enemas (doses) of RBX2660 administered <math>7 \pm 2</math> days apart (the second enema may be administered sooner if CDI diarrhea reoccurs in less than 7 days).

Definition of Treatment Success	Treatment success is defined as: the absence of CDI diarrhea without the need for retreatment with C. difficile anti-infective therapy or fecal transplant through 56 days after completion of study treatment.
Definition of Treatment Failure (CDI Recurrence)	Treatment failure (CDI recurrence) is defined as: 1) the presence of CDI diarrhea, with or without other CDI symptoms, < 56 days after completion of study treatment; 2) a positive stool test for C. difficile ; 3) need for retreatment for C. difficile infection; and 4) no other cause for CDI diarrhea has been determined. [REDACTED]
Determination of Success/Failure	The site investigator makes the determination of success based on: the absence of CDI diarrhea without the need for retreatment with C. difficile anti-infective therapy or FT through 56 days after completion of study treatment. The investigator makes the determination of failure based on 1) the subject's reporting the presence of CDI diarrhea, with or without other CDI symptoms, < 56 days after completion of study treatment; 2) a positive stool test for C. difficile ; 3) need for retreatment for C. difficile infection; and 4) no other cause for CDI diarrhea symptoms is determined.
Medical Monitor Adjudication	The Medical Monitor will adjudicate SAEs and other adverse events of interest to provide an objective, qualified judgment of the events.
Sample Size	[REDACTED] The study will enroll up to approximately 150 subjects to allow for loss-to-follow and additional safety numbers if needed. [REDACTED]
[REDACTED]	[REDACTED]

Blinding	This is an open-label study; no blinding will be employed.
Study Population	The target population is adults ( $\geq 18$ years old) with recurrent CDI who have had either a) at least two recurrences after a primary episode [REDACTED] and have completed at least two rounds [REDACTED] of severe CDI resulting in hospitalization.

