**3.5 Definition of Treatment Success**

Treatment success is defined as: the absence of CDI diarrhea without the need for retreatment with *C. difficile* anti-infective therapy or FT through 56 days after completion of study treatment.

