**3.6 Definition of Treatment Failure**

Treatment failure (CDI recurrence) is defined as: 1) the presence of CDI diarrhea (see Section 3.4), with or without other CDI symptoms,  $< 56$  days after completion of study treatment; 2) a positive stool test for *C. difficile*; 3) need for retreatment for *C. difficile* infection; and 4) no other cause for CDI symptoms has been determined. [REDACTED]

[REDACTED]

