### 3.7 Management of Treatment Failures

Treatment failures (as determined by the site investigator at the time of CDI recurrence) are to be treated with the therapy(ies) deemed most appropriate by their study investigator. All CDIs, including reoccurrences and new episodes, are to be captured in detail on the CDI History and On-study Episodes eCRF.

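### Protocol 6.8's default to success does not match the success definition when a subject is retreated or given fecal transplant without a positive stool test; the day-56 limit also differs between sections

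*Protocol*

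**What the plan says.** - **Success.** Protocol 3.5 and SAP 4.1.3 and 6.5 ask for no CDI diarrhea and no need for CDI retreatment or FT. In 3.5 this covers "anti-infective therapy or FT through 56 days after completion of study treatment". No stool test enters the definition.
- **Failure.** Protocol 3.6 and SAP 4.1.4 equate failure with CDI recurrence and require four things jointly: diarrhea before day 56, then "a positive stool test for *C. difficile*; 3) need for retreatment for *C. difficile* infection; and 4) no other cause for CDI symptoms" found.
- **Visit 4.** When recurrence is suspected before day 56, Protocol 6.8 says that "the investigator assesses for recurrence using the four criteria in Section 3.6". Its next sentence says that the judgement on need for retreatment "in the absence of a positive stool test for *C. difficile* will be made by the study investigator", so that treatment "can be quickly administered in the case of failure to avoid serious adverse events". It then says that if the subject "does not have reoccurrence of CDI before 56 days after completing study treatment, s/he is considered a treatment success (see Section 3.5").
- **Who decides.** The site investigator determines the outcome (Protocol 3.8, SAP 4.1.6) in an open-label study (Protocol 3.9).
- **Window.** The synopsis row on determining the outcome bases success on no need for "anti-infective therapy or FT through 56 days after completion of study treatment. The investigator makes the determination of failure based on" the four criteria. Protocol 3.8 and SAP 4.1.6 describe the same step with a limit of less than 56 days.
- **Populations.** SAP 8.7.1 puts the primary analysis on the Evaluable Population and repeats it on the Full Analysis Set (FAS) and Per Protocol sets. SAP 6.3 foresees subjects given FT before the 8-week follow-up who have no Treatment Failure eCRF. It removes them from the Per Protocol set and lists no such exclusion for the Evaluable Population.

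**The concern.** A binary endpoint needs a rule under which every subject with a known outcome is either a success or not. Here the success and failure definitions leave a gap between them, and Protocol 6.8 appears to fill that gap with success while citing a definition that would not.

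The gap is not hypothetical. Protocol 6.8 itself expects some subjects to be judged in need of retreatment without a positive test, and SAP 6.3 expects some to receive FT with no failure form. An investigator who applies the 6.8 default literally could record a success for a subject whom SAP 6.5 makes a non-success. That would act directly on the primary endpoint.

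The Evaluable Population adds a second route. SAP 6.3 gives as an example of exclusion a subject who leaves before failure is determined and without follow-up to 56 days (day 49 to 63). A subject retreated without a positive test who then leaves early has no four-criterion failure, so could be treated as having no outcome at all.

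**Working it through.** No figure in the plan depends on this point, and the sample-size reasoning is redacted, so there is nothing to reproduce. The check sets the rules side by side and then sizes one recoded subject.

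**Step 1: classify cases under each visible rule.** The literal reading of 6.8 is that success means the four criteria of 3.6 are not all met. Retreated means retreated with a *C. difficile* anti-infective or given FT.

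| Case | Failure (3.6) | Success (3.5) | Success (3.8) | Success (6.8, literal) |
|---|---|---|---|---|
| A. Day 55, CDI diarrhea, no positive test, retreated | no | no | no | **yes** |
| B. Day 55, no qualifying diarrhea, no positive test, retreated | no | no | no | **yes** |
| C. Day 55, all four criteria met | yes | no | no | no |
| D. Day 56, diarrhea, positive test, retreated | no | no | **yes** | **yes** |
| E. Day 55, CDI diarrhea, no positive test, not retreated | no | no | no | **yes** |

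A and B are the main conflict: 6.8 disagrees with the definition it cites. C is consistent everywhere. D isolates the day-56 boundary. E also falls in the gap but is a different question, because nobody judged that retreatment was needed.

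**Step 2: try the milder reading of 6.8.** Suppose reoccurrence in the default sentence is governed by 3.5. Then A and B are non-successes and 6.8 agrees with SAP 6.5. But 6.8 would then be speaking of failure without a positive test, which 3.6 does not allow. The conflict moves from 6.8 against 3.5 to 6.8 against 3.6; it does not disappear.

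**Step 3: list the day-56 limits.**
- Day 56 inside the success window: Protocol synopsis, 2.3, 3.5 and 7.2; SAP 3.3, 4.1.3 and 6.5.
- Day 56 outside: Protocol 3.8 and SAP 4.1.6 for success; Protocol 3.6 and SAP 4.1.4 for failure; Protocol 6.8 for the default.

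**Step 4: size.** For k recoded subjects out of N, the shift in the success rate is 100 × k/N points.
- N=150 (enrolment ceiling, Protocol 8.1 and SAP 4.5): 100 × 1/150 = 0.67 points.
- N=100 (approximate size of the data-received-to-date analysis, Protocol 8.3): 100 × 1/100 = 1.0 point.
- The documents give no value for k. Purely as an assumption, k from 1 to 5 gives 0.67 to 3.3 points at N=150 and 1.0 to 5.0 points at N=100.
- If the same coding recodes one historical control, the control rate moves 100/100 = 1.0 point with 100 controls or 100/200 = 0.5 points with 200 (Protocol A7 gives a minimum of 100 and up to about 200).

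**The case against.** The strongest reply is that 6.8 can be read in harmony with 3.5. Its default sentence does not mention four criteria, it points to 3.5, and the sentence before it ties retreatment without a positive test to failure. SAP 6.5 and 8.7.1 define and analyse treatment success with no stool-test condition, and nothing visible in 8.7.1 derives the endpoint from the failure definition or from 6.8. This reply stands in part: the visible text favours non-success. It does not close the matter, because that reading contradicts the joint criteria in 3.6 and no visible sentence says which rule governs.

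Redaction also limits the point. Text is blacked out after the criteria in Protocol 3.6 and SAP 4.1.4, at the end of 6.8, after the semicolon in SAP 4.1.6, and within SAP 8.7.1. A reconciling rule may stand there. The finding is that visible sentences disagree, not that a rule is absent.

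A reader might go further in three ways that the documents do not support:
- *The plan counts retreated subjects as successes and inflates the result.* Only one literal reading of 6.8 does so, and the SAP definition points the other way.
- *SAP 6.3 keeps FT subjects without a failure form as successes in the Evaluable Population.* It says only that they leave the Per Protocol set; it does not code them.
- *Non-success should simply be the full complement of 3.5.* Protocol 3.4 defines CDI diarrhea by stool count and duration alone. The full complement would therefore also take in diarrhea that was never retreated and was test-negative or had another cause (case E and its like). Protocol 7.2 itself expects some short bouts of diarrhea before day 56.

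It is also fair to say that the day-56 difference touches only events on that one day, and that 150 is a ceiling with an allowance for loss to follow-up, so the Evaluable count may be smaller.

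**Conclusion.** The point holds as an inconsistency in outcome coding that should be reconciled. Success and failure are not complements on the visible text, and a subject retreated or given FT without a positive stool test is classified differently by a literal 6.8 than by 3.5 and SAP 6.5. Under either reading of 6.8, one pair of passages disagrees. The day-56 discrepancy is real but minor.

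The size is known only per subject: 0.67 points at N=150 or 1.0 point at N=100 in the RBX2660 rate. Moving these subjects to non-success can only lower that rate. The net effect on the comparison cannot be derived, because the number of affected subjects is not given and the same coding may also lower the control rate. The 6.8 default itself is a Visit 4 rule for RBX2660 subjects and does not apply to charts.

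The conclusion rests on the visible text alone and would narrow if the redacted sentences already state the rule.

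**What to change.** 1. Reword the default sentence in Protocol 6.8 so that success is determined by meeting 3.5, not by the absence of four-criterion recurrence.
2. State in SAP 8.7.1, or confirm if redacted text already does so, that a subject retreated with a *C. difficile* anti-infective or given FT for CDI within the window is a non-success with a determined outcome in the Evaluable and FAS analyses, whatever the stool test result. Code historical controls by the same rule.
3. Use one day-56 boundary in Protocol 3.5, 3.6, 3.8 and 6.8 and SAP 4.1.3, 4.1.4, 4.1.6 and 6.5.
4. Do not let this change recode diarrhea that was not retreated and was test-negative or had another established cause. The sponsor should state separately how it is coded.

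The Per Protocol exclusion in SAP 6.3 can stay.

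The cost is wording in both documents and one derivation. The data are already planned: under Protocol 3.7, CDI episodes "are to be captured in detail on the CDI History and On-study Episodes eCRF"; SAP 6.1 records concomitant medications at every contact; SAP 6.3 presupposes that FT without a failure form can be identified; and the control chart review in Protocol A4 collects treatments and outcomes for each episode. The downside is that the RBX2660 rate may become slightly less favourable. The change concerns outcome coding only and leaves clinical management as it is.
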